10.2.5 Assessment of Intensity

The investigator will make an assessment of intensity for each AE reported during the study. An intensity grade will be assigned to each AE. The intensity grading scales used in this study are adapted from the “FDA Guidance for Industry: Toxicity Grading Scale for Healthy Adult and Adolescent Volunteers Enrolled in Preventive Vaccine Clinical Trials, September 2007”.

10.2.5.1 Tables for Clinical Abnormalities

10.2.5.1.1 Solicited AR Intensity Grading Scale

Table 10.1: Solicited injection site reactions: terminology, definitions, and intensity scales – Adults

CRF term (MedDRA lowest level term [LLT])	Injection site pain	Axillary swelling	Axillary tenderness	Injection site erythema	Injection site swelling	Injection site induration	Injection site bruising
Diary card term	Pain	Underarm swelling	Underarm pain	Redness	Swelling	Hardening	Bruising
Definition	Pain either present spontaneously or when the injection site is touched or injected limb is mobilized	Axillary (underarm) swelling ipsilateral to the side of injection	Axillary (underarm) tenderness ipsilateral to the side of injection	Presence of a redness including the approximate point of needle entry	Swelling at or near the injection site Swelling or edema is caused by a fluid infiltration in tissue or cavity and, depending on the space available for the fluid to disperse, swelling may be either soft (typically) or firm (less typical) to touch and thus can be best described by looking at the size of the swelling	Hardening at or near the injection site. Hardening is caused by a slow diffusion of the product in the tissue leading to a thick or hard area to touch at or near the injection site and thus can be best described by looking at the size of the hardening.	Bruising is the result of the diffusion of blood in the skin from ruptured blood vessels that forms a purple or black and blue spot on the skin. It can be best described by looking at its size.

Intensity scale*	CRF: Grade 1: A type of adverse event that is usually transient and may require only minimal treatment or therapeutic intervention. The event does not generally interfere with usual activities of daily living. Grade 2: A type of adverse event that is usually alleviated with additional therapeutic intervention. The event interferes with usual activities of daily living, causing discomfort but poses no significant or permanent risk of harm to the research participant. Grade 3: A type of adverse event that interrupts usual activities of daily living, or significantly affects clinical status, or may require intensive therapeutic intervention. Diary card: Grade 1: No interference with activity Grade 2: Some interference with activity Grade 3: Significant; prevents daily activity	Grade 1: ≥ 25 to ≤ 50 mm Grade 2: ≥ 51 to ≤ 100 mm Grade 3: > 100 mm	Grade 1: ≥ 25 to ≤ 50 mm Grade 2: ≥ 51 to ≤ 100 mm Grade 3: > 100 mm	Grade 1: ≥ 25 to ≤ 50 mm Grade 2: ≥ 51 to ≤ 100 mm Grade 3: > 100 mm	Grade 1: ≥ 25 to ≤ 50 mm Grade 2: ≥ 51 to ≤ 100 mm Grade 3: > 100 mm
-------------------------	---	--	--	--	--

MedDRA: Medical Dictionary for Regulatory Activities

* For pain, the scale will be provided in the CRF and the intensity will be transcribed from the diary card. For other injection site reactions (erythema and swelling), the classification as Grades 1, 2, or 3 will be applied at the time of statistical analysis; the scale is provided for information purposes only. The actual size of the reaction will be reported in the CRF.

Table 10.2: Solicited systemic reactions: terminology, definitions, and intensity scales – Adults

CRF term (MedDRA lowest level term [LLT])	Fever	Headache	Malaise	Myalgia	Arthralgia	Shivering	Fatigue	Nausea	Vomiting
Diary card term	Temperature	Headache	Feeling unwell	Muscle aches and pains	Joint pain	Chills	Tiredness	Feeling sick	Vomiting
Definition	Elevation of temperature to $\geq 38.0^{\circ}\text{C}$ ($\geq 100.4^{\circ}\text{F}$)	Pain or discomfort in the head or scalp. Does not include migraine.	General ill feeling. Malaise is a generalized feeling of discomfort, illness, or lack of well-being that can be associated with a disease state. It can be accompanied by a sensation of exhaustion or inadequate energy to accomplish usual activities.	Muscle aches and pains are common and can involve more than one muscle at the same time. Muscle pain can also involve the soft tissues that surround muscles. These structures, which are often referred to as connective tissues, include ligaments, tendons, and fascia (thick bands of tendons). Does not apply to muscle pain at the injection site which should be reported as injection site pain.	Pain in a joint or joints	Cold feeling	Overall feeling of tiredness or lack of energy	Feeling of sickness with inclination to vomit	Forceful expulsion of the contents of the stomach via the mouth or sometimes the nose; emesis. Vomiting does not include spitting up.
Intensity scale*	Grade 1: $\geq 38.0^{\circ}\text{C}$ to $\leq 38.4^{\circ}\text{C}$,	CRF: Grade 1: A type of adverse event that is usually transient and may require only minimal treatment or therapeutic intervention. The event does not generally interfere with usual activities of daily living.							

or $\geq 100.4^{\circ}\text{F}$ to $\leq 101.1^{\circ}\text{F}$
 
Grade 2: $\geq 38.5^{\circ}\text{C}$ to $\leq 38.9^{\circ}\text{C}$,
 
or $\geq 101.2^{\circ}\text{F}$ to $\leq 102.0^{\circ}\text{F}$
 
Grade 3: $\geq 39.0^{\circ}\text{C}$
 
or $\geq 102.1^{\circ}\text{F}$
	
Grade 2: A type of adverse event that is usually alleviated with additional therapeutic intervention. The event interferes with usual activities of daily living, causing discomfort but poses no significant or permanent risk of harm to the research participant.
 
Grade 3: A type of adverse event that interrupts usual activities of daily living, or significantly affects clinical status, or may require intensive therapeutic intervention.
 
Diary card:
 
Grade 1: No interference with activity
 
Grade 2: Some interference with activity
 
Grade 3: Significant; prevents daily activity

---	---

MedDRA: Medical Dictionary for Regulatory Activities

* For all reactions (except fever), the scale will be provided in the CRF and the intensity will be transcribed from the diary card. For fever, the body temperature will be recorded, and the classification as Grade 1, 2, or 3 will be assigned at the time of the statistical analysis based on the unit used to measure the temperature and the intensity scale.

Important notes for the accurate assessment of temperature:

Participants are to measure body temperature once per day, preferably always at the same time. The optimal time for measurement is the evening, when body temperature is the highest. Temperature is also to be measured at the time of any apparent fever. The observed daily temperature and the route of measurement are to be recorded in the diary card, and the highest temperature will be recorded by the site in the CRF. The preferred route for this study is oral.

10.2.5.1.2 Unsolicited AE Intensity Grading Scale

For measurable unsolicited AEs that are part of the list of solicited reactions, the corresponding scale for solicited reactions will be used (see [Section 10.2.5.1.1](#)).

All other unsolicited AEs will be classified according to the following intensity scale:

- Grade 1
 - CRF: A type of adverse event that is usually transient and may require only minimal treatment or therapeutic intervention. The event does not generally interfere with usual activities of daily living.
 - Diary card: No interference with activity.
- Grade 2
 - CRF: A type of adverse event that is usually alleviated with additional therapeutic intervention. The event interferes with usual activities of daily living, causing discomfort but poses no significant or permanent risk of harm to the research participant.
 - Diary card: Some interference with activity.
- Grade 3
 - CRF: A type of adverse event that interrupts usual activities of daily living, or significantly affects clinical status, or may require intensive therapeutic intervention.
 - Diary card: Significant; prevents daily activity.

10.3 Appendix: Risk-based Approach

ICH E6-R2 guideline for GCP is introducing the « risk-based approach » concept which permits to focus efforts on what is critical for a study and most specifically on Critical Data and Critical Processes. Critical data and processes are defined for the study with associated risks in the Study Risk Management Plan.

10.4 Appendix: Abbreviations

ACIP	Advisory Committee on Immunization Practices
AE	Adverse Events
AESI	Adverse events of special interest
AR	Adverse reactions
BL	blood sample
CRF	Case report form
DMC	Data Monitoring Committee
FAS	Full analysis set
GBS	Guillain-Barré syndrome
GCI	Global Clinical Immunology
GCP	Good Clinical Practice
GM	geometric mean
GMT	geometric mean of titers
GPV	Global Pharmacovigilance
HA	Hemagglutinin
HAI	Hemagglutinin inhibition
HRT	Hormonal replacement therapy
IB	Investigator's Brochure
ICF	informed consent form
ICH	International Council for Harmonisation
IDMC	Independent Data Monitoring Committee
IEC	Independent Ethics Committees
IM	intramuscular
IMP	Investigational Medicinal Product
IRB	Institutional Review Boards
LLOQ	lower limit of quantification
LNP	lipid nanoparticle
MA	memory aid
MAAE	medically attended adverse event
MedDRA	Medical Dictionary for Regulatory Activities

NIAID	National Institute of Allergy and Infectious Diseases
NIH	National Institutes of Health
NIMP	Non- Investigational Medicinal Product
PPAS	Per-protocol analysis set
PV	Pharmacovigilance
PT	Preferred Term
RMO	Responsible Medical Officer
SAE	Serious adverse events
SafAS	Safety Analysis Set
SAP	Statistical analysis plan
SoA	Schedule of Activities
SOC	System Organ Class
SUSAR	suspected unexpected serious adverse reactions
TBD	to be determined
ULOQ	upper limit of quantification
WHO	World Health Organization
VAC	vaccination

Type of design	3-arm study with either concomitant or single administration of Fluzone High-Dose Quadrivalent vaccine and Moderna COVID-19 Vaccine
Phase	II
Control method	Active-controlled (single administration versus coadministration)
Study population	Adults 65 years of age and older
Level and method of blinding	Open-label
Study intervention assignment method	Randomization
Number of participants	300 participants 65 years of age and older
Intervention groups	Participants will be randomly assigned to 1 of the 3 study groups in a 1:1:1 ratio, corresponding to i) concomitant administration of Fluzone High-Dose Quadrivalent vaccine and Moderna COVID-19 Vaccine, ii) administration of Fluzone High-Dose Quadrivalent vaccine alone, and iii) administration of Moderna COVID-19 Vaccine alone
Total duration of study participation	Approximately 180 days (6 months after vaccination) for all participants
Countries	United States
Use of an Independent Data Monitoring Committee, Dose Escalation Committee, or similar review group	No

Table 1.2: Schedule of activities (simplified compared to the protocol)

Phase II Study, 2 Visits, 2 Telephone Contacts, either 1 or 2 Vaccination, 2 Blood Samples, 180 Days' Duration Per Participant

[figure not shown]
Visit (V)	Collection of information in the CRF	V01	Telephone contact (TC1)	V02	TC2 6-Month Safety Follow-up
Study timelines (days [D])		D01	D08	D22	D181
Time interval (days)			V01 + 7 days	V01 + 21 days	V01 + 180 days
Time windows (days)			[+2 days]	[+3 days]	[+14 days]
Visit procedures:					
Informed consent	X	X			
Inclusion/exclusion criteria	X	X			
Collection of demographic data	X	X			
Collection of medical history *	X Significant Medical History	X			
History of seasonal influenza and COVID-19 vaccination	X	X			
Randomization / Allocation of participant number	X	X			
Blood samples (BL) for Ab assays (20 mL) ‡	X	BL0001		BL0002	
Vaccination (VAC)	X	VAC1 (all groups) VAC2 (Group 1)			
Immediate surveillance (30 min)	X	X			
Collection of solicited injection site and systemic reactions	X	Up to 7 days after vaccination			
Collection of unsolicited AEs	X	Up to 21 days after vaccination			
Collection of concomitant medications	X Reportable concomitant medication	X		X	
Collection of SAEs, AESIs, and MAAEs ‡‡	X	To be reported at any time during the study			
End of Active Phase participation record***	X			X	
End of 6-month safety follow-up ***					X

Abbreviations: Ab, antibody; AE, adverse event; AESI, adverse event of special interest; BL, blood sample (#); CRF, case report form; D, Day; DC, diary card; SAE, serious adverse event; AESI, adverse event of special interest; MAAE, medically-attended adverse event; SARS-CoV-2, severe acute respiratory syndrome coronavirus 2; V, Visit; VAC, Vaccination.

* Including history of COVID-19 infection.

- † Targeted physical examination will be performed at V01. If needed, targeted physical examination based on medical history and Investigator's discretion might be performed at the other vaccination visit(s).
- ‡ BL0001 must be collected before vaccine injection. Participants that consent to Future Research by ticking the corresponding box in the ICF will provide a 20 mL of blood instead of 10 mL for each BL0001 and BL0002.
- § Participants will use DC1 to record information about solicited reactions, unsolicited AEs, SAEs, and AESIs from D01 to D08 after vaccination and will continue to record information about unsolicited AEs, SAEs, and AESIs from D09 to D22.
- ** The Investigator or an authorized designee will remind the participants to bring back the DC at the next visit and will answer any questions.
- †† The Investigator or an authorized designee will interview the participants to collect the information recorded in the DC1 and will attempt to clarify anything that is incomplete or unclear.
- ‡‡ AESIs (serious and non-serious) will be collected throughout the study as SAEs to ensure that events are communicated to the Sponsor in an expedited manner and followed up until the end of the follow-up period or resolution, as per the assigned causal relationship. Full list of AESIs is available in Section 8.3.6 of the protocol.
- *** Participants will be in the Active Phase from enrollment (D01) until completion of V02 and in the 6-Month Safety Follow-Up from completion of V02 until approximately 6 months after V01.

Figure 1.1: Graphical study design

Detailed design is provided in Sections 4.1 and 1.2 of the protocol.

2 Objectives and Endpoints

Table 2.1: Objectives and endpoints

Objectives	Endpoints
Safety Objective	

 To describe the safety profile of Fluzone High-Dose Quadrivalent vaccine and Moderna COVID-19 Vaccine administered concomitantly or singly, up to 21 days after injection in each study intervention group. 	
 Presence of immediate unsolicited systemic adverse events (AEs) reported in the 30 minutes after injection Presence of solicited (pre-listed in the participant's diary card [DC] and CRF) injection site reactions and systemic reactions occurring up to 7 days after injection Presence of unsolicited AEs reported up to 21 days after injection Presence of serious adverse events (SAEs) reported up to 6 months after injection Presence of adverse events of special interest (AESIs) reported up to 6 months after injection Presence of medically-attended AEs (MAAEs) reported up to 6 months after injection
Immunogenicity Objectives	
1) To describe the immune response elicited by Fluzone High-Dose Quadrivalent vaccine administered concomitantly or singly, in each study intervention group.	Endpoints for Immunogenicity Objective #1 
 Hemagglutination inhibition (HAI) individual titer on Day (D) 01 and 21 days after injection of Fluzone High-Dose Quadrivalent vaccine (D22) Individual HAI titers ratio D22/D01 Detectable HAI titer, ie, with a titer ≥ 10 (1/dil) at D01 and 21 days after injection of Fluzone High-Dose Quadrivalent (D22) Seroconversion (titer < 10 [1/dil] at D01 and post-vaccination titer ≥ 40 [1/dil] at D22, or titer ≥ 10 [1/dil] at D01 and a ≥ 4-fold-rise in titer [1/dil] at D22) HAI titer ≥ 40 (1/dil) on D01 and 21 days after injection of Fluzone High-Dose Quadrivalent (D22)
2) To describe the immune response elicited by Moderna COVID-19 Vaccine administered concomitantly or singly, in each study intervention group.	Endpoints for Immunogenicity Objective #2 
 Individual anti-S binding IgG concentration on D01 and 21 days after injection of Moderna COVID-19 Vaccine (D22) Individual anti-S binding IgG concentration ratio

	D22/D01
	
• 2-fold-rise and 4-fold-rise in anti-S binding IgG concentration 21 days post-injection D01

3 Statistical Considerations

3.1 Statistical Hypothesis

No hypothesis testing will be performed in this study.

3.2 Sample Size Determination

The study will enroll approximately 300 participants 65 years of age or older: approximately 100 participants will be concomitantly administered of Fluzone High-Dose Quadrivalent vaccine and Moderna COVID-19 Vaccine (Group 1), approximately 100 participants will be administered Fluzone High-Dose Quadrivalent vaccine alone (Group 2), and approximately 100 participants will be administered Moderna COVID-19 Vaccine alone (Group 3).

3.3 Populations for Analyses

For the purposes of analysis, the following analysis sets are defined:

Participant Analysis Set	Description
Randomized	All participants that have a randomization number
Safety Analysis Set (SafAS)	Participants who received at least 1 dose of study vaccine. All participants will have their safety analyzed according to the vaccine they actually received and study intervention group. Safety data recorded for a vaccine received out of the protocol design will be excluded from the analysis (and listed separately).
Immunogenicity analysis set (IAS)	Subset of randomized participants who received at least 1 dose of study vaccine. Participants will be analyzed according to the vaccine they actually received and study intervention group.

3.4 Statistical Analyses

3.4.1 General Considerations

All statistical analyses will be performed under the responsibility of the Sponsor's Biostatistics Platform using the SAS® software, Version 9.4 or above (SAS Institute, Cary, North Carolina, USA).

For descriptive purposes, the following statistics will be presented:

Table 3.1: Descriptive statistics produced

Disposition and follow-up description	Categorical data	At least number of participants (Percentage of participants are also possible).
	Continuous data	Mean, standard deviation, minimum and maximum.
Baseline characteristics	Categorical data	Number of participants. Percentage of participants.
	Continuous data	Mean, standard deviation, quartiles, minimum and maximum.
Clinical safety results	Categorical data	Solicited: Number and percentage (95% CIs for main endpoints) of participants. Unsolicited: Number and percentage (95% CIs for main endpoints) of participants and number of events.
Immunogenicity results	Categorical data (seroconversion, cutoff)	Number and percentage (95% CIs for main endpoints) of participants.
	Continuous data (titer / concentration)	Log10: Mean and standard deviation. Anti-Log10 (work on Log10 distribution, and anti-Log10 applied): Geometric mean, 95% CI of the geometric mean, quartiles, minimum, and maximum. Graphical representation by Reverse Cumulative Distribution Curve (RCDC).

The confidence interval (CI) for the single proportion will be calculated using the exact binomial method (Clopper-Pearson method, quoted by Newcombe (1), i.e., using the inverse of the beta integral with SAS®).

For immunogenicity results, assuming that Log10 transformation of the titers / data follows a normal distribution, at first, the mean and the 95% CI will be calculated on Log10 (titers / data) using the usual calculation for normal distribution (using Student's t distribution with n-1 degree of freedom), then antilog transformations will be applied to the results of calculations, in order to provide geometric means (GMs) and their 95% CI.

For each participant, randomized study group will be assigned from the randomization number assigned to the participant, and injected vaccine/study group will be derived from the label of the vaccine(s) injected on D01, as collected in the CRF.

3.4.2 Safety Endpoints

The SafAS will be used. Safety will be assessed in all 3 study groups, however the assessment of the safety of the co-administration with regards to single administration will focus on groups 1 and 3, as influenza vaccine is expected to be less reactogenic.

Safety endpoints will be summarized, with 95% CI for the main endpoints, by actual study group. Injection site reactions will be summarized by actual study group and vaccine received; for subjects having received the 2 concomitant administrations, injections site reactions will be assigned to one of the 2 vaccines according to the side of vaccination/reaction.

In terms of contents, solicited reactions will be presented by time to onset, maximum severity, number of days of occurrence and action taken; unsolicited AEs will be presented by causal relationship, time of onset, maximum severity and duration; SAEs will be presented by causal relationship, seriousness and outcome.

Subgroup analyses will also be performed as complementary analyses; in particular, the main safety endpoints will be described according to gender and age group, as appropriate according to number of participants in the respective subgroups.

3.4.3 Immunogenicity Endpoints

The IAS will be used. Immunogenicity endpoints will be summarized with 95% CI by actual study group and vaccine received, for each timepoint. Cumulative distribution frequencies will also be provided to support that concomitant vaccine administration does not interfere with the assay readout, particularly at the extremes of high and low titer results.

In addition, the ratios of post-vaccination GMTs between concomitant and single injections will be presented for the five antigens with 2-sided 95% CIs. A baseline adjustment will be applied using an ANCOVA model of the D22 log10 titer/concentration with vaccine group and D01 log10 titer as factor and covariate, respectively.

Subgroup analyses will also be performed as complementary analyses; in particular, immunogenicity will be described according to serostatus at baseline (pre-vaccination < or >= to LLOQ), previous influenza vaccination, gender and age group, as appropriate according to number of participants in the respective subgroups.

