6.3 Measures to Minimize Bias: Randomization and Blinding

6.3.1 Randomization and Allocation Procedures

Participants will be randomized in a 1:1:1 ratio into Group 1, Group 2, and Group 3, using a permuted block method with stratification by site and by age group (< 75 years and \geq 75 years).

The full detailed procedures for randomization are described in the Operating Guidelines.

Participant numbers will be 12 digits long, with a 3-digit country identifier, a 4-digit study center identifier, and a 5-digit participant identifier. The 5-digit participant identifier will correspond to the chronological order of enrollment in the center within each stratum. For example, Participant 8400001-00001 is the first participant enrolled in Center Number 1 (in the US) and Participant 8400002-00002 is the second participant enrolled in Center Number 2 (in the US), within the < 75 years stratum.

Participant numbers should not be reassigned for any reason. The randomization codes will be kept securely in an internal system.

The Biostatistics platform of the Sponsor will provide randomization lists that will be printed as scratchable lists. These lists will mention the randomization order of the participant and the corresponding study group covered by a silver-colored patch. The Investigator will scratch off the list to know the study group. Once scratched, each randomization line will be dated and signed by the Investigator or the sub-investigator in charge of administering the study intervention(s).

Each participant will be vaccinated with the study intervention(s) corresponding to the group mentioned on the randomization list. If the dose initially taken for the vaccination is broken or cannot be used, the Investigator will take another dose of the same study intervention

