9.2 Sample Size Determination

The study will enroll approximately 300 participants 65 years of age or older: approximately 100 participants will be concomitantly administered of Fluzone High-Dose Quadrivalent vaccine and Moderna COVID-19 Vaccine (Group 1), approximately 100 participants will be administered Fluzone High-Dose Quadrivalent vaccine alone (Group 2), and approximately 100 participants will be administered Moderna COVID-19 Vaccine alone (Group 3).

No study power calculation was conducted for this study. Assuming a drop-out rate of 5%, a total of 95 evaluable subjects per study group is anticipated.

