9.4 Statistical Analyses

The statistical analysis plan (SAP) will be finalized prior to database lock and it will include a more technical and detailed description of the statistical analyses described in this section. This section is a summary of the planned statistical analyses of the most important endpoints including primary and key secondary endpoints.

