9.4.3 Other Analysis

The ratios of post-vaccination GMTs between concomitant and single injections will be presented for the five antigens with 2-sided 95% CIs.

Subgroup analyses will also be performed as complementary analyses; in particular, immunogenicity will be described according to serostatus at baseline, previous influenza vaccination, and age, as appropriate according to number of subjects in the respective subgroups.

Other analyses will be described in the SAP.

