4.2.4 Derived Other Variables

4.2.4.1 Age for Demographics

The age of a participant in the study will be the calendar age in years at the time of inclusion, as collected in the eCRF.

For randomization stratification and subgroup analyses, the 2 following classes of age will be used: < 75 years and ≥ 75 years.

5 Changes in the Conduct of the Trial or Planned Analyses

This section summarizes major changes in the SAP amendment.

Table 5.1: Major statistical changes in SAP amendment

Amendment Number	Approval Date	Changes	Rationale
Amendment 1 (SAP v2.0)		Addition of 6-month f-up analysis	Protocol Amendment 2

6 Supporting Documentation

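### The GMT-ratio ANCOVA leaves out the randomisation strata (site and age group); if these predict D22 beyond D01, its 95% CIs are somewhat conservative

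*SAP*

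**What the plan says.** Protocol 6.3.1 allocates participants 1:1:1 "using a permuted block method with stratification by site and by age group", with a cut at 75 years. The block size and the number of sites are not given.

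Protocol 9.4.3, under Other Analysis, plans the between-group comparison: "The ratios of post-vaccination GMTs between concomitant and single injections will be presented for the five antigens with 2-sided 95% CIs". It names no model. SAP 3.4.3 supplies one: "A baseline adjustment will be applied using an ANCOVA model of the D22 log10 titer/concentration with vaccine group and D01 log10 titer". Vaccine group is the factor and the D01 value is the covariate.

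The SAP knows of the age stratum. Section 4.2.4.1 states: "For randomization stratification and subgroup analyses, the 2 following classes of age will be used". Age group is then used only to describe subgroups (SAP 3.4.2 and 3.4.3). Site appears in no planned analysis. No sensitivity model adds either factor.

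On precision, Protocol 9.2 says: "No study power calculation was conducted for this study". It expects 95 evaluable participants per group after 5% drop-out. Both documents state that no hypothesis is tested.

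**The concern.** Stratified permuted blocks balance the arms within site and age group. If those factors are related to the D22 response, this balance lowers the true variance of the difference between arms. A model without the strata does not take credit for that. It leaves their variation in the residual, so its standard error is too large and its nominal 95% interval covers more than 95% of the time.

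The GMT ratios are the only between-group estimates with CIs in the plan; everything else is summarised group by group. With about 95 participants per arm and no power calculation, the width of these five intervals largely sets what the study can say about interference between the two vaccines. Only precision is at stake: the point estimate is not biased, and the error runs in the cautious direction.

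**Working it through.** **The plan's own figure.** 100 × (1 − 0.05) = 95 evaluable per group, as Protocol 9.2 states. There is no power or margin to reproduce.

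**Large-sample size of the effect.** Let R² be the share of the D22 residual variance, given D01, that site and age group explain. With arms balanced within strata:

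- strata-adjusted width / planned width = √(1 − R²)
- actual coverage of the planned interval = 2Φ(1.96/√(1 − R²)) − 1

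| R² | Adjusted CI narrower by | Actual coverage of planned CI |
|---|---|---|
| 0.02 | 1.0% | 95.2% |
| 0.04 | 2.0% | 95.4–95.5% |
| 0.10 | 5.1% | 96.1% |
| 0.20 | 10.6% | 97.2% |

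**On the ratio scale.** Assume a residual SD of 0.45 log10 after D01. The SE is 0.45 × √(2/95) = 0.0653. With t(187) ≈ 1.973 the half-width is 0.129, so the CI is the ratio multiplied or divided by 10^0.129 ≈ 1.345. At R² = 0.10 the half-width is 0.129 × √0.90 = 0.122, a factor of about 1.325. For other SDs the factors at R² 0, 0.10 and 0.20 are:

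- SD 0.4: 1.30, 1.28, 1.27
- SD 0.5: 1.39, 1.37, 1.34
- SD 0.6: 1.49, 1.46, 1.42

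**Finite-sample check by simulation.** The limit assumes complete blocks and known stratum effects, so the realistic case was simulated. From the documents: N = 300, 1:1:1 allocation, permuted blocks within site by age group, 5% drop-out. Assumed: SD 0.45, 30% aged ≥75, 10 to 25 sites, blocks of 3 or 6, a quarter of the stratum effect due to age, 3,000 trials per setting. The planned ANCOVA was compared with the same model plus age group and a REML random site intercept.

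| R² | Change in log-scale CI width | Coverage, planned model |
|---|---|---|
| 0 | 0.3–0.4% narrower (no real gain) | 94.8–95.4% |
| 0.02 | 1.0–1.1% narrower | not tabulated |
| 0.04 | 1.8–1.9% narrower | 95.2–95.7% |
| 0.10 | 4.4–4.7% narrower | 95.5–96.4% |
| 0.20 | 9.2–9.7% narrower | 96.3–97.0% |

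Coverage of the adjusted model was 94.3–95.3% over the grid, and the mean estimate was within 0.003 log10 of the truth throughout.

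One setting in full (15 sites, blocks of 3, R² 0.10): the planned model's mean SE was 0.0652 against an actual SD of the estimate of 0.0616, so the SE was 0.0652/0.0616 − 1 = 5.8% too large. The half-width fell from 0.1286 to 0.1226 (factor 1.345 to 1.326), and coverage moved from 96.4% to 95.1%.

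**Robustness.**

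- Fitting all three arms in one model gives changes of −0.3%, −4.6% and −9.7% at R² 0, 0.10 and 0.20.
- If the whole stratum effect is due to age, age group alone narrows the CI by 1.0%, 2.0% and 5.2% at R² 0.02, 0.04 and 0.10.
- A simulation that included 3 and 5 sites gave 0.2–0.5% narrower at R² 0, 4–5% at 0.10 and 8–10% at 0.20, with adjusted coverage of about 94–96%. The random intercept therefore does not fail when sites are few.
- Site as fixed effects would widen the CI at R² 0 by 0.35% (10 sites) up to 2.4% (25 sites).

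**The case against.** The best case for the plan is that this hardly matters. The study is descriptive, the ratios are listed as a supplementary analysis, and the planned interval never covered materially below 95%, so no reader is led into false certainty. The relevant R² is what site and age explain after D01, and D01 already absorbs any effect that runs through baseline. Nothing in the documents supports an R² of 0.10 or 0.20. Even at 0.10, a ratio of 1.0 would have an interval of about 0.74–1.35 rather than 0.75–1.33, which changes no descriptive reading. Immunogenicity is also described by age group, so an age effect would be visible.

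All of that stands as a limit on importance. It does not justify the omission, which is unexplained and can be corrected at almost no cost. A description by age subgroup does not alter the standard error of the ratio.

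Timing is the other objection. Protocol 9.4 says "The statistical analysis plan (SAP) will be finalized prior to database lock", but the SAP is already an amended version 2.0 with no approval date shown, and the immunogenicity data are analysed before the final D181 safety data. The documents do not show whether those data had been released. If they had, replacing the main model in an open-label trial would be post hoc. This objection also stands, and the fix is worded to respect it.

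**Conclusion.** The point holds. The randomisation is stratified by site and age group, the model for the GMT ratios contains neither, and no reason is given. If the strata predict D22 beyond D01, the planned CIs are conservative: about 1–2% too wide on the log scale at R² 0.02–0.04 and roughly 4–10% at R² 0.10–0.20, with actual coverage up to about 97%. If they do not predict it, the planned intervals are correct as they are.

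The direction follows from the design. The size rests on assumed values for the SD, the number of sites, the block size, the age mix and R², none of which the documents give. There is no bias and no decision rule is affected, so this is a worthwhile refinement and not a flaw that endangers the study's conclusions.

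**What to change.** Before database lock, and before the immunogenicity data are analysed, amend SAP 3.4.3 to specify: D22 log10 value on vaccine group, D01 log10 value and age group (<75, ≥75 years) as fixed effects, with site as a random intercept. State the estimation method (REML) and the degrees-of-freedom method. State also that if the site variance is estimated as zero, the model reduces to the ANCOVA with age group. Keep the present model as a sensitivity analysis. If immunogenicity results have already been seen, keep the present model as the main one, report the stratum-adjusted model as a sensitivity analysis, and say when it was added.

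The cost is one model statement, one fixed-effect degree of freedom and one variance component. If site and age prove uninformative, the interval stays within about 0.4% of its planned width (allow up to about 1%). A random intercept is preferred to fixed site effects because the latter could cost up to 2.4% with 25 sites and no site effect.
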